1.0 Study Summary

Study Title	Stay Active
Study Design	Experimental Intervention
Primary Objective	To compare the impact of two physical activity interventions on student's physical activity.
Secondary Objective(s)	
Research Intervention(s)/ Investigational Agent(s)	Two arms: Arm 1: classroom based physical activity Arm 2: classroom based physical activity plus family support for physical activity.
IND/IDE #	
Study Population	Up to 15 classrooms from Kansas City area elementary schools.
Sample Size	Up to 250 Students, 250 parent(s)/guardian(s), and 15 teachers
Study Duration for Individual Participants	1 semester (for about 4 months)
Study Specific Abbreviations/ Definitions	CBPA: classroom based physical activity

2.0 Objectives

- 2.1** The pilot study will create, implement, and evaluate a physical activity program in both the school and home setting during the COVID-19 pandemic.

3.0 Background

- 3.1** COVID-19 has created numerous challenges to children's ability to engage in healthy lifestyles. The need for physical distancing creates barriers to many types of physical activity children typically engage in. The school setting is an essential source of children's physical activity and the recent move of school education from in-person to online eliminated over half of children's daily physical activity. Since the COVID-19 pandemic is accelerating socioeconomic disparities, which have major implications for long term health, it is more important than ever to provide safe opportunities for children from low-income families to engage in active lifestyles.

The 2020-2021 school year in the Kansas City area will create numerous challenges to teachers and other school personnel. Whether classes will be conducted online, in-person, or using a mix of the two approaches is still unknown, but all approaches will substantially limit opportunities for children to engage in healthy lifestyles. Schools will be forced to constantly adapt to new procedures that prevent the spread of infection. These challenges will make it even more difficult for elementary schools to support children's health and physical activity.

In addition to supporting health, the activities reenergize students and improve attention, learning, and positive behavior in the classroom. Teachers are trained and supported to deliver additional activities throughout the week, but our physical activity leaders minimize burden on the teachers as we acknowledge that teachers are in a particularly challenging situation due to the pandemic.

4.0 Study Endpoints

- 4.1** The primary endpoints are daily step counts and daily physical activity minutes.
- 4.2** The secondary endpoints are parent and teacher perceptions.

5.0 Study Intervention/Investigational Agent

[figure not shown]
- 5.1** This study will be conducted in in-school and out-of-school settings.
- 5.2** Arm 1 (CBPA):

SHORT TITLE: Stay Active

- CBPA: Physical activity support is provided by integrating daily structured activities in the classroom delivered by physical activity leaders through a video conferencing platform in partnership with the classroom teacher. Activities last about 10 minutes or less and have the flexibility of being integrated with academic lessons or serving as a break from academics.

The activities are simple and get kids moving in place. The activities will be delivered by a research staff member via video conferencing (using the schools preferred platform). A combination of live activities led by the research team and pre-recorded videos will be used (see example below). If live videos do not work for the teacher, they will have the option to only use the pre-recorded videos or receive a list of resources to promote CBPA in their classrooms.

Teachers will be asked to complete weekly a weekly REDCap survey to track the amount of CBPA they offered to their class outside of the time study staff provided physical activity support. Teachers will also be asked to complete one post-study survey and interview to provide their perceptions of the Stay Active program.

Study staff will provide an optional training session for teacher to walk through the importance of CBPA, as well as accessing the resources that will be provided to them. This training will be accessible through live videoconference or a PowerPoint presentation sent via email.

5.3 Arm 2 (CBPA plus family):

- CBPA component will be identical to above.
- Family Component: A newsletter, with supporting handouts and resources for the family to use, will be sent to parents or guardians once every two weeks over the semester and posted on the study website. The newsletters include physical activity information related to safety/protection, skills building, motivation, overcoming barriers, and goal setting and monitoring. The handouts include optional worksheets and physical activity tracking sheets to support families. As part of the program, children also receive a Garmin wearable physical activity monitor. Parents or guardians will receive text messages with behavior change messages based on the Garmin data. Text messages also contain links to website materials. Parents/Guardians of students who receive a Garmin will receive text reminders about wearing the device if no steps or minutes of physical activity are being detected.

Texts will be sent out using the Twilio platform.

Participants (both parent and child) will be asked to complete two surveys during the study. Surveys ask questions related to general demographics, household physical activity habits, and COVID-19 related questions. The first survey has been submitted in the SmartForm (Baseline Survey_Version_0.02), the second survey will be submitted later as an amendment, as it is still being developed.

6.0 Procedures Involved

6.1 Data Collection Procedures

- Describe the method for identifying candidates for the study
 - School Recruitment: We will work with district contacts to identify schools and classrooms to participate. School staff will be provided an informational letter about the study.
 - Participant Recruitment: A recruitment flyer will be sent to families via their classroom teacher.
- Describe the procedure for obtaining data
 - Teachers will receive weekly emails containing a brief REDCap survey to complete.
 - Teachers will complete a post intervention survey (we will submit this later as an IRB amendment, as it is still being developed).

SHORT TITLE: Stay Active

- Teachers will complete a post intervention interview (we will submit this later as an IRB amendment, as it is still being developed).
- If the teacher withdraws from the study, their class will no longer be able to participate in the Arm #1 of the study.
- Parents or guardians will complete a pre- and- post intervention survey, with the options of on paper or over RedCap. The post intervention survey will be submitted later as an IRB amendment, as it is still being developed.
- Students in both arms will be asked to wear Garmin physical activity devices to provide physical activity information throughout the intervention. The Garmin is worn like a wristwatch. The device is small and non-intrusive. The Garmin device is a consumer wearable that will automatically detect and track activity such as walking, running, and cycling.
- Study staff will set up the Garmin account with an email address provided by the parent and a generic password. This information will be shared in the Participant Garmin Instructions sent in the mail along with the Garmin device. Study staff will not input any personal information, aside from the provided email address, while creating the Garmin account.
- Students can participate in the CBPA portion of the study without opting in to wearing the Garmin device. This participant will not be consented or assented but will still receive the classroom physical activity lessons via their classroom.
- Students who neither opt out or opt in to the study will be allowed to participate in the CBPA portion of the study. No personal information or data will be collected from these students.
- Any potential participant that opts out of the CBPA portion of the study will be told that they can watch, engage in a separate activity, or leave the session temporarily.
- No data aside from that which is already being collected via the Garmin devices will be collected from the physical activity sessions.
- Two-way video conferencing will be used to deliver physical activity study, but sessions will not be recorded by study staff. Study staff is will be joining an existing video meeting set up by the school (meetings that are already being used by the school). Staff will not set up the meeting platforms for the physical activity sessions.

- No personal information will be recorded in the recruitment phase prior to a participant enrolling in the study.
- Garmin devices, device set up and participant information, along with a hardcopy of surveys if requested by the participant will be sent to the provided mailing address of the participant. Mailing address is collected during the consent process and will be stored securely in REDCap.

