8.0 Genetic Analysis Information

8.1 N/A

9.0 Sharing of Results with Subjects

9.1 Parents or Guardians of students in Arm #2 will receive weekly text messages with updates on the students overall physical activity and previous weeks step count. Step and minutes of physical activity information from the Garmin data may also be shared with the PE teachers. Information will be aggregate and will not contain any identifiers.

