14.2 Participants

- A recruitment flyer will be sent out via multiple modes of communication to all families of 4th and 5th grade students in

classrooms of selected teachers that are participating. The recruitment flyer will be sent by the teacher.

- The recruitment flyer will describe the CBPA as all students in the classroom (even those who do not wear the Garmin device) will be able to participate in the CBPA if desired. The recruitment flyer will explain that such students/families can opt out of receiving the CBPA by contacting the study team or their teacher. These students will not complete any study assessments.
- The recruitment flyer will also describe the Garmin assessment portion of the study and the potential family content that half of the classrooms will be randomized. To enroll in the Garmin portion of the study participants will need to opt in by contacting the study team. Thus, these are the study participants who will be consented/assented and measured/assessed.
- Research staff will respond via email or telephone to inquiries generated by the recruitment email and flyer. The research team will go over the details of the study with potential participants over the phone or email. If a potential participant says they want to enroll in the study after receiving the study information, having any questions answered by the research team member, and being confirmed as eligible, the parent and child will be consented and assented over the phone. E-consent will then officially take place over the phone and REDCap. The participant will receive a copy of the P/A/C form and participant instructions by e-mail or in the mail.

14.3 We will have access to parent names, email addresses, and phone numbers prior to obtaining permission/assent. We are requesting a waiver of HIPAA authorization for recruitment purposes only. We will not retain any data from potential participants who do not enroll in the study.

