15.0 Reimbursement, Payment and Tangible Property provided to subjects

15.1 Classroom teachers who complete the post intervention assessments will receive a Greenphire ClinCard in the amount of \$50.

15.2 Participants will receive up to \$50 for participating. The cash card will be issued at the end of the fall semester. \$25 will be given to participants who wear the Garmin device the first week of the study. Another \$25 will be given to participants who wear the device the last week of the study and complete the final survey, which is completed by the parent and child. In addition to the cash card, the participant will be able to keep the Garmin device at the end of the program, which is valued at \$80.

15.3 The research team will collect the required information (e.g. address and date of birth) for issuing compensation after P/A/C has been obtained during the P/A/C appointment. This information will be immediately entered into Greenphire by the research team and then shredded to protect confidentiality. Payment will be issued to the participant when they complete the study and complete the final survey.

15.4 If the participant chooses to withdraw at any point during the study, they will not be asked to return the Garmin device. They will be compensated for each portion of the study they complete.

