25.0 Permission/Accent/Consent Process

25.1 Arm 1: The recruitment flier allows parents/students to opt out of the CBPA portion of the study and to opt in to the Garmin assessments and potentially receiving the family component of the intervention (if randomized to the second study arm). P/A/C for the family component would then follow the process for Arm 2.

Non-English speakers will be able to call the study line to have the recruitment flyer read to them by an interpreter. A list of those who opt out of the CBPA portion of the study will be kept on secure CM servers for the duration of the study and will then be deleted.

We will obtain permission/assent/consent for teachers but will not document permission/assent/consent in writing, and have developed a permission, assent and or consent scripts (e.g., Study Information Sheet) as applicable and uploaded them in myIRB in lieu of full permission/assent/consent forms. We have reviewed HRP-411 - CHECKLIST - Waiver of Written Documentation of Consent to ensure that we have provided sufficient information.

25.2 Arm 2: The study team will obtain permission/assent/consent via eConsent Lite on the potential participants smart device over the phone:

- The p/a/c process will take place via telephone and will follow CM research policy ([10.05 Telephone Process](#)).
- The potential participant will have a chance to ask questions and decide if they'd like to participate.
- The Study team will be following [CM research policies on informed permission/assent/consent](#).
- [name] research team, as well as the study coordinator or other research staff listed on the IRB may complete consent
- Time devoted to consent will be will only consist of an eConsent conversation over the phone.
- Participants and their families will be given plenty of time to consider participation (they can decline to participate during the consent phone call and request follow up) as well as ask any questions they have.
- Study staff will explain each main section of the p/a/c form as well as provide a summary. Checking for understanding while going through the form and after.

Subjects who are not yet adults (infants, children, teenagers)

- The study team will consider participants in the sample of 4th and 5th graders not yet adults.
- One parent will provide permission, even if the other parent is alive, known, competent, reasonably available, and shares legal responsibility for the care and custody of the child.

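### Could the teacher-withdrawal rule in section 6.1 end follow-up of whole classrooms in one arm only?

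*Combined protocol and SAP*

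**What the plan says.** The rule is one bullet in section 6.1: "If the teacher withdraws from the study, their class will no longer be able to participate in the Arm #1 of the study".

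The label has two uses in the same document.

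- **Comparison arm.** The summary in section 1.0 lists "Arm 1: classroom based physical activity" against a second arm that adds family support. Section 5.2 follows this, and section 5.3 says of the second arm that the "CBPA component will be identical to above". Section 9.1 uses the matching label: "Parents or Guardians of students in Arm #2 will receive weekly text messages".
- **Classroom track.** Section 25.1 opens with "Arm 1: The recruitment flier allows parents/students to opt out of the CBPA portion of the study" and goes on to teacher consent. The flyer goes to all families in the selected classrooms, so this use comes before allocation and applies whatever the allocation turns out to be.

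On outcome data, section 6.1 states: "Students in both arms will be asked to wear Garmin physical activity devices to provide physical activity information throughout the intervention". Section 16.2 keeps data gathered before a withdrawal and stops further collection from the subject who withdrew. Section 20.4 specifies mixed models with time nested in participants and participants in classrooms, comparing pre-to-post change between the groups. It names no analysis set.

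**The concern.** Allocation is by classroom; section 14.2 refers to "potential family content that half of the classrooms will be randomized". With at most 15 classrooms, each one is a sizeable part of its arm. If Arm #1 in the withdrawal rule means the randomised group, the rule removes a class allocated to CBPA alone and says nothing about a class in the other arm, although both receive the same classroom activity. If staff also took removal to mean that the devices and the final survey stop, one arm could lack post-intervention data for whole classrooms while the other did not. If the classes that left differed in activity change from those that stayed, the between-arm contrast would be biased.

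On either reading, no sentence states what happens to the Garmin and survey data of consented students in that class. Two readers might therefore handle the same classroom differently.

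**Working it through.** The plan gives no figure to reproduce: section 20.3 bases the sample size on resources, and no teacher withdrawal rate appears. The check is mainly a comparison of texts.

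**Step 1: which sense fits the rule.** The teacher tasks in sections 5.2 and 6.1 are to host classroom activity, log it weekly and report on the programme afterwards. Section 25.1 places teacher consent under its Arm 1 heading. Classroom activity is the same in both arms, so a teacher's departure affects its delivery in either. A rule that applied to one randomised group only would leave the other arm's classes with the same activity, no teacher and no rule. The classroom-track sense avoids that oddity, and under it no one-arm loss arises.

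**Step 2: does the rule stop outcome collection?** Its wording concerns the class taking part. The step from there to switching off devices and surveys is not in the text. The other sections point the other way:

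| Element | Where | Does it need the teacher after enrolment? |
|---|---|---|
| Device wear in both arms, throughout | 6.1 | No |
| Opt-in and consent through the study team | 14.2, 25.2 | No |
| Devices, and paper surveys on request, mailed to the participant | 6.1 | No |
| Data drawn through the Garmin API | 20.5 | No |
| Second payment, for those "who wear the device the last week of the study and complete the final survey, which is completed by the parent and child" | 15.2 | No |
| Collection ends for the subject who withdraws | 16.2 | No: section 13.2 counts teachers and students separately |

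Taken together, these make continued collection the default for a consented student who has not withdrawn.

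**Step 3: what a complete loss would cost.** Assume 15 classrooms split 8 versus 7, equal class sizes, and total loss of the class. The average class is at most 250/15 = 16.7 students. One class is 1/8 = 12.5% or 1/7 = 14.3% of its arm. The standard error is proportional to sqrt(1/a + 1/b), where a and b are the classrooms per arm.

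- No loss: sqrt(1/8 + 1/7) = 0.5175.
- One lost from the smaller arm: sqrt(1/8 + 1/6) = 0.5401, up 4.3%. Two lost: sqrt(1/8 + 1/5) = 0.5701, up 10.2%.
- One lost from the larger arm: sqrt(1/7 + 1/7) = 0.5345, up 3.3%. Two lost: sqrt(1/6 + 1/7) = 0.5563, up 7.5%.
- With 10 classrooms, 5 per arm (an assumption, since 15 is a maximum): 0.6325 rises to 0.6708 with one lost (6.1%) and to 0.7303 with two (15.5%).

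These are not strict upper limits, because classes may be unequal. With no intraclass correlation, arms of 133 and 117 students, and a class of 25 lost from the smaller arm, the ratio is sqrt(1/133 + 1/92) / sqrt(1/133 + 1/117) = 0.1356/0.1268, up about 7.0%.

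**Step 4: bias.** If a lost class differs by D from the rest of its arm, the observed arm mean moves by D/7 or D/8. That is the realised shift from one loss. It becomes an expected bias only if withdrawal is related to activity change. The documents give no value for D and no reason to expect such a relation, so no figure in steps per day can be supported.

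**The case for a change.** The best case for a change is that the authors had a clearer term available. Later bullets in section 6.1 speak of the CBPA portion when that is meant, and another uses arms in the comparison sense, so a strict reader may take Arm #1 as the randomised group. The bullet also sits under the prompt on obtaining data, which could suggest that it governs data collection. Continued follow-up is feasible, and stating it would take a few words.

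Some of this stands: the label is inconsistent, and no sentence expressly says that collection continues. It does not show that the plan, followed in the ordinary way, loses data. The harm needs the less natural sense of the label, plus an inference from taking part to being measured, plus withdrawals related to activity change. Section 5.2 also lets a teacher for whom live sessions do not work use recorded videos only or a resource list, which removes one obvious reason to withdraw. The lack of a named analysis set in section 20.4 applies to every participant and is not a defect of this rule.

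**Conclusion.** No change to the plan follows. The wording is a clerical looseness together with an unstated default that the remaining sections supply: outcome collection continues for individually consented students who have not themselves withdrawn, and comparison between the intervention groups is naturally read as comparison by allocation. The documents show no one-arm loss of follow-up.

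If a whole class were nevertheless lost, the standard error would rise by 3% to 4% with 15 equal-sized classrooms, or about 6% with 10. It would rise somewhat more if the lost class were large. For a pilot sized by resources, that is a small cost. The conclusion rests on staff reading section 6.1 together with sections 14 to 16, and on there being no evidence that teacher withdrawal would be common or would differ by arm. What happens to the classroom programme itself after a teacher leaves is for the sponsor to decide.

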20.2 General Design Issues

- Pre-post between group comparison

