20.4 Data Analyses

- Mixed effects models will account for nesting of time within participants and participants within classrooms. Changes in PA from pre to post will be compared between the intervention groups.

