20.5 Secure Storage of Data

- Garmin data will be obtained through the Garmin API. It will show each student's daily minutes of physical activity and step counts when participants were wearing the device. Participant also have access to this information through their Garmin Connect account. As part of the consent/assent process study staff will describe that information from the devices will be

collected through the Garmin API and that Garmin will have access to this information.

Garmin data are stored on Garmin servers and will be accessed by the research team via the Garmin web apps on CMH secure computers. Study staff will not provide Garmin access to participant names or any other PHI that would make a participant readily identifiable. Reports will be aggregated across the participants so no participant will be identifiable, and no identifiable data will be published or presented.

Online surveys will be managed in REDCap.

To protect the security of responses on hardcopy surveys, participants will complete a confidential survey that includes a participant identification number on the form. The participant ID#, rather than name, will be recorded on hardcopy surveys. A master list containing the names and associated IDs will be kept securely in REDCap. No one except the study team members will have access to this master list. Names and descriptions of participants will not be published or reported. All data will be stored without identifiers, and only participant number. Survey data are entered on Children's Mercy computers and will be stored in REDCap. Research team members are trained to not divulge participants' information in anyway.

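### Does the pre-to-post comparison of Garmin activity lack a usable 'pre' period because the wear windows are not defined?

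*Combined protocol and SAP*

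**What the plan says.** The primary endpoints are daily steps and daily activity minutes (sections 4.1 and 20.1). The Garmin feed supplies each student's "daily minutes of physical activity and step counts when participants were wearing the device" (section 20.5). Section 20.2 gives the design as "Pre-post between group comparison". Section 20.4 adds: "Changes in PA from pre to post will be compared between the intervention groups". It also gives the model: "Mixed effects models will account for nesting of time within participants and participants within classrooms". Neither section names the days that make up 'pre' or 'post'.

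On the wear schedule, section 6.1 states: "Students in both arms will be asked to wear Garmin physical activity devices to provide physical activity information throughout the intervention". Section 15.2 splits the payment in two. The first $25 "will be given to participants who wear the Garmin device the first week of the study", and the second $25 "will be given to participants who wear the device the last week of the study and complete the final survey". The survey is the only measure whose timing is stated outright: "Parents or guardians will complete a pre- and- post intervention survey" (section 6.1).

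**The concern.** A change score needs a starting value that treatment has not yet touched. Read literally, section 6.1 has students wearing the device during delivery, and nothing readable places the first wear week before the first classroom session or newsletter. The first and last weeks appear only as payment conditions, not as analysis windows. Because the model nests time within participants without saying how time is coded, several choices of window would comply with the text.

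Two things would be at stake. First, any Arm 2 effect already present on the 'pre' days is subtracted from the contrast, which normally pulls the result toward no difference. Second, a baseline from before delivery cannot be collected once delivery has started.

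**Working it through.** The plan states no figure to reproduce: section 20.3 bases the sample size on resources and gives no effect size, SD or power. The check is therefore which effects survive in the contrast, and how large the overlap could be.

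**What the contrast estimates.** Let C be the effect of the classroom sessions, identical in both arms (section 5.3), and F the added effect of the family component in Arm 2. Assume that they add. Then

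- Arm 2 change = (C_post + F_post) − (C_pre + F_pre)
- Arm 1 change = C_post − C_pre
- Difference in change = F_post − F_pre

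Classroom sessions that start before or during the 'pre' days cancel. Season and school-calendar effects common to both arms also cancel. The share of the Arm 2 effect lost is F_pre / F_post, so only family content acting during the 'pre' window matters.

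**What family content can act in week 1.** Section 5.3 bases the behavior-change texts on Garmin data, and section 9.1 has weekly texts reporting the previous week's steps. Both need prior wear. Wear reminders are not counted here, since they prompt wearing rather than activity. That leaves a newsletter, sent every two weeks, if the first one goes out in week 1.

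**Size with the first week as 'pre' and the last week as 'post'.** Inputs:

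- Duration: about 4 months (section 1.0), taken as 16 weeks (assumption).
- Newsletters: one every two weeks (section 5.3), so 16 / 2 = 8.
- Feedback texts: weekly (section 9.1), from week 2 (assumption, since each looks back one week), so 15.
- Total family contacts: 8 + 15 = 23.
- Response proportional to cumulative contacts (assumption).

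Results:

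| First newsletter | Contacts by end of week 1 | Contacts by end of week 16 | Share lost |
|---|---|---|---|
| Week 1 | 1 | 23 | 1/23 = 4.3% |
| Week 2 | 0 | 23 | 0/23 = 0% |

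With 17 weeks and a week-1 newsletter there are 9 + 16 = 25 contacts, and the share is 1/25 = 4.0%.

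**Sensitivity to the response shape.** If the effect begins only after 4 weeks and then grows linearly, the share lost is 0%. If it rises from day 1 with a half-life of 4 weeks, evaluated at mid-week:

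- Week 1: 1 − 0.5^(0.5/4) = 0.083
- Week 16: 1 − 0.5^(15.5/4) = 0.932
- Share lost: 0.083 / 0.932 = 8.9%

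The last shape is severe, because it has the family effect acting before any feedback text could have been sent.

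**The case for a change.** The strongest reply is that a payment rule does not define an analysis. Someone could take the first and last halves of the semester as 'pre' and 'post' and still comply with section 20.4. Under the same contact model, mean cumulative contacts would then be 5.5 against 17.5, or 6 against 18, so 31% to 33% of the effect would be lost. The arithmetic stands, but the documents name no such window. The only wear weeks they single out are the first and the last, and the study pays to secure data in exactly those weeks.

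A second reply is that objective 2.1 is to evaluate the program, and a within-arm change would miss any classroom effect already present in 'pre'. That is true of such an analysis, but the plan specifies none. Its stated primary objective (section 1.0) is to compare the two interventions.

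A third is that the order of wear and delivery is not written down. That cannot be held against the plan here. Section 10 has separate rows for data collection and for the intervention, and their shading, like the section 5 figure, is missing from the copy reviewed. Month columns would not identify individual wear days, so what remains of this point is the missing definition of the windows, not a demonstrated lack of baseline.

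**Conclusion.** No change is needed. The text leaves out a detail that analysts would sensibly fill with the first and last paid wear weeks. On that reading the between-arm contrast loses about 0% to 4% of the Arm 2 effect under the cumulative-contact assumption, and about 9% under a deliberately fast response. Any loss is normally toward no difference, so it would not create a false benefit.

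Two features of the design limit the damage even if the first week is not clean. Classrooms are randomized to the family component (sections 14.2 and 25.1), so a comparison of later wear days between arms remains valid, though less precise. The mixed model in section 20.4 can treat early and late days as repeated outcomes, so students without early data can stay in the analysis.

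The conclusion rests on four assumptions: the classroom sessions are delivered alike in both arms, their effect and the family effect add, feedback texts follow at least a week of wear, and the windows are the first and last weeks. For a pilot sized on available resources, the remaining uncertainty does not alter what the trial can conclude about the two arms.
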